## 1. SCIENTIFIC BACKGROUND

Red blood cell concentrates (RBC) is the most frequently transfused blood component. The transfusion trigger for the product varies between different countries and different centres [1], as does the dosage (number of units) transfused under similar conditions [2]. Many centres experience a blood shortage periodically, and this may threaten patient safety and postpone planned operations [3]. The usual assumption used in the clinical practice is that a single unit of red blood cells transfused to an adult should result in an increment in circulating hemoglobin of 1 g/dl [4]. This practice is, however, based on an estimate on the basis of units, or at best volume.

Furthermore, there is an existing difference depending on which type of RBCs is transfused; whole blood, filtrated RBCs, buffy coat removed RBCs or filtrated and buffy coat removed RBCs. This will decrease the hemoglobin levels in the unit by approximately 10 %, 10 % and 20 % respectively.

Many have discussed the advantage of standardizing the units of RBCs [5-7].

Two different concepts are proposed; one is to standardise the unit, the other is to adjust the hemoglobin dose according to the patient's blood volume, called hemoglobin dosing.

Unfortunately, the total hemoglobin content of the units does not represent a homogeneity [5], and the blood volume of the patients vary as well [8]. Högman & Knutson performed a red cell apheresis study, demonstrating it was possible to collect either one or two units of RBCs without exceeding 13 percent of any donor's blood volume, provided the collected volume of blood in each unit was less than the current standard [5]. Applying a standard at 45g of RBC Hb per unit was found to permit the collection of maximum RBC Hb and plasma in the evaluated population of Scandinavian donors (standardised units). Hemoglobin dosing requires information on the hemoglobin content of each unit to be transfused, as well as the patients' height, weight and actual and desired hemoglobin levels.

In a study from Turkey, Arslan et al showed that matching the hemoglobin dose to the individual needs of the patient may reduce the total usage of red cell concentrates by approximately 30 % [9]. Calculating the patients' total need of hemoglobin to achieve the targeted hemoglobin level made this possible. The hemoglobin dose was defined as hemoglobin concentration in the donor multiplied with donation volume. However the success rate was closely linked to patients' weight; increased weight correlated with unwanted outcome. In this study the total amount of transfused RBCs was reduced to 72 from the original 104 units required.

Holme et al have recently published data indicating that currently used formulas for estimation of a person's red cell volume (RCV) by weight and height are decades old and were based on the use of (51)Cr isotopes and on a sample population, which may not be reflective of today's population [10]. Their study demonstrated that (99m) Tc is a reproducible and precise method for determination of a person's RCV and that current formulas may significantly overestimate the RCV of today's population. This is likely the result of a shift in population characteristics over the past four decades as reflected by an increased mean body mass index (from 25 to 28 kg/m^2), which has not resulted in a proportionally increased RCV.

Although measuring of hemoglobin in the unit would represent the gold standard for the actually hemoglobin content in the unit, other methods can also be used. Preliminary data from Canada, Scotland and Norway have detected a close correlation between the hemoglobin content in the unit and the weight of the unit ([name], [name], [name], [name], [name], unpublished). This will allow us to simplify the methods used in the departments of immunology and transfusion medicine. By just measuring the weight of each unit, we can easily correlate and calculate the actually hemoglobin content in each unit.

Studies have also indicated that the quality of the blood probably will be reduced with the storage time in the blood bank [11, 12]. In future studies we will also be able to correlate the hemoglobin increment to the age (days from donations) of the unit. This will bring information to the postulated theory of reduced function and survival of older RBCs versus newer RBCs [11, 12]. The blood volume have traditionally been calculated after standard formulas (e.g. Dubois and Dubois), but recent studies have suggested use of other formulas, which are probably more relevant for the population today [10].

On the basis of this existing data, we have performed a pilot study to assess the feasibility of a multicentre study on hemoglobin dose and patient matching ([name], [name], [name], [name], and [name], submitted). Patients administered for day-treatment with transfusion with RBCs at different centers in Norway, Scotland and Canada, were included in the study. Their hemoglobin concentration was measured before and after transfusion.

We found that the hemoglobin content in RBC units showed considerable heterogeneity. By correlating the hemoglobin increment with the patients' weight or blood volume we found no significant correlation. However, when correlating the total hemoglobin dose given with the hemoglobin increment, we found a significant correlation. Furthermore, an even stronger correlation was found when the hemoglobin increment was correlated to hemoglobin dose divided with the patients' estimated blood volume ([name], [name], [name], [name], and [name], submitted). Our study has made a contribution to the question about feasibility of hemoglobin dosage.

As a result of variation in transfused blood volume and the blood donors' hemoglobin concentration, besides the differences in the RBC preparation, the hemoglobin content in the final unit is far from standardized.

New and better technologies in combination with new findings and experience have made it possible to achieve a higher degree of standardization. However, we still need further and larger studies on this area to make a conclusion about the feasibility and the clinical impact of the method. Therefore we want to go on with a randomized clinical trial on hemoglobin dose and patient matching to bring further information about the question about feasibility and possibility of hemoglobin dosage and standardization of the RBCs.

## **2. OBJECTIVES AND STUDY DESIGN**

This is a randomized clinical study on hemoglobin dose and patient matching. The aim of the study is to evaluate whether the targeted hemoglobin increment (2 grams per decilitre) in the patient can be predicted from the hemoglobin dose/weight of the blood bag transfused. In the test group, the hemoglobin dose needed will be calculated, whereas in the control group, the prescribed number of red cell units will be transfused.

## **3. PATIENTS**

Patients will be hospital in or out-patients, recruited by the investigator, who require transfusions of red cell concentrates and who fulfill the inclusion criteria.

### **a. Inclusion Criteria**

- Patients receiving red cell transfusions or expected to receive one or more red cell transfusions
- Patients over 16 years of age
- Patients for whom height and weight information is available
- Patients who have consented to participate

### **b. Exclusion Criteria**

- Patients who are hemodynamically unstable (ongoing bleeding or hemolysis)
- Patients with a known hemolytic anemia (congenital or acquired)

- Patients with a positive Direct Antiglobulin Test (DAT)
- Patients for whom informed consent has not been obtained
- Patients where the hemoglobin concentration increment target is above 2g/dl.
- Patients with auto- or alloantibodies against RBCs.

**c. Patient Enrolment**

Patients who meet the inclusion criteria will be invited to participate, and those who provide informed consent will be enrolled in the study. Patients will be randomized to standard transfusion or patient matched hemoglobin dosing transfusion based on the weight of the blood bag.

**d. Patient Consent Procedure**

The purpose and procedures of the study will be explained to prospective participants and their written consent obtained prior to their taking part in the study. The patients will also be informed that they have the right to withdraw from the study at any time, without giving a reason, and this will not affect their future treatment in any way.

## **4. TRANSFUSION PROCEDURE**

Patients will be transfused according to local practice for their clinical condition and may receive more than one red cell unit, up to a maximum of three units per transfusion. Multiple units must be transfused consecutively with no disruption in the procedure.

Data may be collected on more than one transfusion procedure for each patient, to allow assessment of factors affecting hemoglobin increment between and within patients.

## 5. DATA COLLECTION

### a. Baseline Data Collection

#### i. *Patient Baseline Demographic Data*

The following information will be collected for all participating patients:

- Age
- Gender
- Weight
- Height
- Primary diagnosis
- ABO and Rh (D) blood type

### b. Pre-Transfusion Data Collection

#### i. *Patient Data*

Prior to transfusion the following data will be collected for the patient:-

- Indication for transfusion
- Hemoglobin level (within 24 hours prior to transfusion)

#### ii. *Product Data*

Prior to transfusion the following data will be collected for the red cell unit(s) to be transfused:

- ABO and Rh type
- Weight of the red cell unit(s)
- Age of the red cell unit(s)

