### c. Transfusion Data Collection

The following data will be recorded for each transfusion:

- Time transfusion started
- Time transfusion completed.
- Number of red cell units transfused (maximum 3 units)

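### Does leaving preparation type out of the product data stop the trial from answering its question?

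*Protocol*

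**What the plan says.** Section 1 of the protocol (Scientific Background) names four kinds of red cell product and says of the three processed ones: "This will decrease the hemoglobin levels in the unit by approximately 10 %, 10 % and 20 % respectively". Later in the section, after collection volume and donor hemoglobin have been given as sources of variation, it adds: "besides the differences in the RBC preparation, the hemoglobin content in the final unit is far from standardized". Between these statements it introduces bag weight as the practical measure of content, because data from Canada, Scotland and Norway "have detected a close correlation between the hemoglobin content in the unit and the weight of the unit".

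The design follows that choice. Section 2 asks whether the targeted increment "can be predicted from the hemoglobin dose/weight of the blood bag transfused". Section 3c describes the test arm as "patient matched hemoglobin dosing transfusion based on the weight of the blood bag". Section 4 allows data from more than one transfusion per patient "to allow assessment of factors affecting hemoglobin increment between and within patients".

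The product data in section 5b.ii are ABO/Rh type, "Weight of the red cell unit(s") and age of the unit. Section 5d.ii repeats weight for units not weighed beforehand. Section 5c adds start and completion times and "Number of red cell units transfused (maximum 3 units"). No list in section 5 includes preparation type or a measured unit hemoglobin.

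**The concern.** The protocol puts a number on one product factor and then does not record it, while unit age, for which it gives no number, is recorded. The test arm is dosed from bag weight. If two preparations have different hemoglobin at the same weight, the calculated dose will be wrong for at least one of them. Should the test arm then miss 2.0 g/dl, the listed data could not show whether the weight method or the product mix was responsible. An analysis plan cannot add a term for a variable nobody recorded, so the point cannot be set aside as detail for the SAP.

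The possible size also looks serious next to the planned difference. A 10% dose error on a 2.0 g/dl target is 0.20 g/dl, about half of the 0.38 g/dl in section 6a. If the whole test arm fell short by that much, the expected difference would drop to 1.80 − 1.62 = 0.18 g/dl and power at 55 per group to about 27%.

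**Working it through.** **Inputs.** From section 6a: control mean 1.62 g/dl, target 2.0 g/dl, SD 0.7, 55 episodes per group. From section 1: relative unit content of 1.0 (unprocessed), 0.9 (filtered), 0.9 (buffy coat removed) and 0.8 (both). The protocol states neither alpha nor power; two-sided 5% is assumed throughout.

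**The plan's own figure.** Difference = 2.0 − 1.62 = 0.38. With 80% power assumed, the normal approximation gives n = 2 × (1.960 + 0.842)² × 0.7² / 0.38² = 53.3, rounded up to 54. The t-test version gives 54.2, so 55. The stated 55 reproduces; power at 55 per group by t-test is 80.5%.

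**Is there a contradiction?** The background statements on preparation are reasons why counting units is a poor way to dose. They support dosing by content, and weight is then offered as the measure of content. Sections 2 and 3c apply that choice. Section 4 says only that repeat episodes may be recorded, and why; it does not mention preparation or promise an analysis by product. The product factor that section 1 singles out for correlation with the increment is unit age. It places that work in future studies, and unit age is on the list. So no stated analysis lacks its variable.

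**Case 1: mixed preparations, conversion right on average, weight capturing none of the difference.** The dose error is then noise in the test arm. For an equal mix, added SD = 2.0 × (SD of relative content / mean relative content), divided by √2 when an episode has two independently mixed units. Total SD = √(0.7² + added SD²). Power is from a Welch t-test with only the test arm inflated.

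| Mix | Two units per episode: added SD / total SD / power | One preparation per episode: power |
|---|---|---|
| 1.0 and 0.9 | 0.074 / 0.704 / 80.3% | 80.1% |
| 0.9 and 0.8 | 0.083 / 0.705 / 80.3% | 80.0% |
| 0.9, 0.9, 0.8 | 0.077 / 0.704 / 80.3% | 80.1% |
| all four types | 0.111 / 0.709 / 80.1% | 79.6% |
| 1.0 and 0.8 | 0.157 / 0.717 / 79.6% | 78.6% |

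Against 80.5%, the largest loss is 1.9 percentage points.

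**Case 2: the whole test arm receives a product one step away from the one behind the conversion, again with weight capturing none of it.**

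- Transfused product poorer than the calibration product: 2.0 × (1 − 0.9/1.0) = 0.20 and 2.0 × (1 − 0.8/0.9) = 0.22 g/dl too low, or 53% and 58% of 0.38.
- Transfused product richer: 2.0 × (1.0/0.9 − 1) = 0.22 and 2.0 × (0.9/0.8 − 1) = 0.25 g/dl too high, or 58% and 66% of 0.38. This widens the difference between arms.

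The shift can therefore go either way. It is zero if there is one product with its own conversion, and smaller to the extent that weight reflects the loss. The protocol reports a close correlation but gives no coefficient.

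**Would the field help?** Doses are set before transfusion, so recording the preparation does not undo a wrong dose or restore power. For explaining a shortfall, take SD 0.7, independent episodes, one preparation each and an even split:

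- Test arm only, 27 against 28: SE = 0.7 × √(1/27 + 1/28) = 0.189; 95% half-width 0.38 g/dl.
- Both arms, 55 against 55: SE = 0.7 × √(2/55) = 0.133; half-width 0.26 g/dl.

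Both half-widths exceed the largest one-step shift, 0.25 g/dl. Moreover, if every unit in the trial were of one mismatched product, the field would be constant and could show nothing.

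**The case for a change.** The strongest argument is that whether weight suffices is the very thing being tested, so it should not be assumed when the data fields are chosen. The protocol names no product, section 6e refers to more than one enrolling centre, and the weight correlation comes from unpublished data from three countries, with no statement of which preparations it covers. One field per unit from the blood-bank record would cost almost nothing, and the site code in section 6c stands in for it only if product follows site.

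Much of this is true. The field is absent, a single product is not stated, and no look-up of blood-bank records is planned, although one might still be possible. If the residual SD after allowing for dose per blood volume were 0.5 (an assumption), the even-split half-widths would narrow to 0.27 and 0.19 g/dl, so with both arms pooled a one-step difference could just come into view. The extreme contrast of unprocessed against doubly processed units would be larger, 2.0 × (1 − 0.8) = 0.40 g/dl, but nothing shows that unprocessed units will be used.

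What stands is that the field would be cheap and could help describe the results. It does not follow that the plan is wrong without it. Several centres do not imply several products, and data from three countries may already span preparations. If weight predicts poorly because products differ, that is a legitimate negative answer about the weight method as used. Finding the reason is an exploratory question that section 2 does not ask.

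**Conclusion.** The concern does not hold. Preparation type is missing from the lists, but the protocol neither misstates nor contradicts anything by leaving it out. Weight-based dosing is a declared choice, the randomised comparison is unaffected, and the question in section 2 is answered by the data that are collected.

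Trouble would need either a mix of preparations or a product that does not match the conversion, and in addition a weight measure that misses the difference. The protocol shows none of these. With a conversion that is right on average, the cost is at most about 2 percentage points of power. With a fully missed one-step mismatch, the mean shifts by 0.20 to 0.25 g/dl in either direction, which the extra field could not correct and, at SD 0.7, could not reliably establish.

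These figures assume a two-sided 5% test, SD 0.7, independent episodes and the approximate 10/10/20% reductions in section 1. Recording preparation type would be a reasonable addition, but it is a preference for one more covariate and not a correction the plan needs.

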### c. Transfusion Data Collection

The following data will be recorded for each transfusion:

- Time transfusion started
- Time transfusion completed.
- Number of red cell units transfused (maximum 3 units)

#### **d. Post Transfusion Data Collection**

##### *i. Patient Data*

Patients will have a blood sample taken (preferably from the arm contralateral to the transfusion site) between 15 minutes and 8 hours post completion of transfusion. In the case of transfusion of multiple units, this sample will be taken after the final unit has been transfused. The following data will be recorded:

- Hemoglobin level

##### *ii. Product Data*

- Weight of each red cell unit transfused (if not performed prior to transfusion)

## **6. ADMINISTRATION**

### **a. Sample size and Randomisation procedure**

The patients will be randomized to two groups, the test group receiving a calculated hemoglobin dose and a control group receiving the prescribed number of red cell units. Based on experience, the average hemoglobin increment in the control group will be 1.62 g/dl with a standard deviation of 0.7. To be sure to detect a difference between 1.62 g/dl and 2.0 g/dl hemoglobin increment, 55 transfusion episodes must be included in each group. To allow for 10% missing data, we will include 61 episodes in each group.

The randomization itself is performed by a computer programme.

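### Section 6a counts transfusion episodes although patients are randomised: 55 (61) per group can be filled with repeat episodes, with no allowance for within-patient correlation

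*Protocol*

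**What the plan says.** Section 3c makes the patient the unit of allocation: "Patients will be randomized to standard transfusion or patient matched hemoglobin dosing transfusion based on the weight of the blood bag". Section 6a repeats that patients are randomised to two groups, then sets the size in another unit: "To be sure to detect a difference between 1.62 g/dl and 2.0 g/dl hemoglobin increment, 55 transfusion episodes must be included in each group". The only increase applied is for incomplete data: "To allow for 10% missing data, we will include 61 episodes in each group".

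Section 4 allows repeats: "Data may be collected on more than one transfusion procedure for each patient, to allow assessment of factors affecting hemoglobin increment between and within patients". It sets no maximum per patient.

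The protocol gives no number of patients, does not say whether repeat procedures count toward 55 or 61, and does not mention correlation between increments from the same patient. Section 6a also omits the significance level and the power.

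**The concern.** Two episodes from one patient usually carry less information about a group difference than one episode from each of two patients, because they share that patient's characteristics. A size derived for independent observations holds only if each counted observation comes from a different patient, or if repeat increments are uncorrelated.

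Read literally, section 6a is satisfied by 61 patients with one episode each, or by about half as many with two each. These are different trials. Section 6a is the only basis given for expecting the trial to separate 1.62 from 2.0 g/dl. If repeats fill the quota, the comparison is weaker than that section implies, and a null result could be taken as evidence against hemoglobin dosing when the trial had too few patients to show a difference.

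**Working it through.** **Inputs from section 6a.** Control mean 1.62 g/dl, target 2.0 g/dl, SD 0.7 (stated for the control group), equal groups, 10% missing data.

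**Assumed, because not stated.** Two-sided alpha of 5%; SD 0.7 in both groups; m, the mean number of episodes per patient; ICC, the correlation between increments from the same patient, taken as 0.1, 0.3 and 0.5.

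**Step 1: reproduce 55.** The difference is 2.0 − 1.62 = 0.38, so d = 0.38/0.7 = 0.543. The normal approximation for 80% power gives n = 2 × (1.960 + 0.842)² / 0.543² ≈ 53.3, rounded up to 54. The two-sample t-test needs n = 54.2, rounded up to 55; its power is 79.8% at 54 and 80.5% at 55. So 55 is the smallest independent-observations size that reaches 80%, and it contains no correlation allowance. Other conventional settings do not fit: by the normal approximation, one-sided 5% needs 42 for 80% power and 59 for 90%, and two-sided 5% needs 72 for 90%.

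**Step 2: reproduce 61.** 55/0.9 = 61.1 and 55 × 1.1 = 60.5. Either route gives about 61, so the whole increase is the missing-data allowance. With 10% lost, 61 × 0.9 = 54.9, which is back to about 55.

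**Step 3: effect of counting repeats.** Design effect DE = 1 + (m − 1) × ICC; effective size n_eff = 55/DE; power from the t-test at n_eff per group.

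| m | ICC | DE | n_eff | Power |
|---|---|---|---|---|
| 1 | any | 1 | 55 | 80.5% |
| 1.25 | 0.1 | 1.025 | 53.7 | 79.6% |
| 1.25 | 0.3 | 1.075 | 51.2 | 77.6% |
| 1.25 | 0.5 | 1.125 | 48.9 | 75.7% |
| 2 | 0.1 | 1.1 | 50.0 | 76.7% |
| 2 | 0.3 | 1.3 | 42.3 | 69.4% |
| 2 | 0.5 | 1.5 | 36.7 | 63.0% |

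**Step 4: sensitivity.**

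- *Unequal numbers per patient.* Take 33 patients with one episode and 11 with two (33 + 22 = 55 episodes, mean 1.25). With n_eff = 33 + 22/(1 + ICC) = 53.0, 49.9, 47.7, power is 79.1%, 76.6%, 74.6%. This is close to the m = 1.25 rows.
- *Correlation in the control group only.* With 55 in the test group and 55/DE in the control group, m = 2 gives 78.6%, 74.8%, 71.2%. The loss is smaller but still present.
- *All 61 episodes complete.* At m = 2 the size holds 80% only while 61/(1 + ICC) is at least 54.2, that is, up to an ICC of about 0.125. At ICC 0.3, n_eff = 61/1.3 = 46.9 and power is 74%.

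**The case against.** The strongest reply is that repeats were never meant to count. Section 4 says only that repeat data may be collected, and gives them a purpose of their own that is not the comparison of the two groups. Section 6b speaks of one possible extra blood sample, which fits a single study episode per patient, though weakly. On this reading 55/61 means patients and the size is adequate. The reading is reasonable, but the protocol does not state it. Both sentences in section 6a that set the size count episodes, and nothing excludes repeats from that count.

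A second reply is that the loss has no anchor in the protocol, since m and ICC are both assumed. That stands. With few repeats the loss is a few points at most. Dosing matched to the patient may also remove some between-patient variation in the test group, so a common ICC in both groups may overstate the loss; the control-only calculation shows by how much. The figures show what hangs on the counting rule. They do not predict the trial's power.

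A third reply is that a statistical analysis plan, which may exist but is not available here, could handle clustering. It could settle the analysis model. A clustered analysis does not restore power lost to having fewer patients, and section 6a itself fixes the size, its unit and its only inflation.

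**Conclusion.** The point holds as a fault in how section 6a fixes the unit of the sample size. The count is in episodes, randomisation is by patient, repeats are allowed without limit, and 55 is exactly an independent-observations size. If repeats count, and increments from the same patient are positively correlated, 55 episodes give less power than implied. Over assumed ICCs of 0.1 to 0.5 this is 76–80% at a mean of 1.25 episodes per patient and 63–77% at 2, against 80.5% with one each. These figures rest on a two-sided 5% test, SD 0.7 in both groups, and assumed m and ICC.

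A reader might infer two stronger conclusions that the protocol does not support. One is that the trial is underpowered. That follows only if repeats count, which is not stated; with one episode per patient there is no loss. The other is that the test will exceed its nominal type I error. That depends on whether the analysis ignores clustering, and the protocol leaves the method open, so no such claim is made here.

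**What to change.** In section 6a, state that 55 (61 with missing data) counts one transfusion episode, the first, per randomised patient, and that later episodes serve only the between- and within-patient question in section 4.

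If the sponsor intends repeats to count, keep 61 episodes but give the expected m and the assumed ICC, restate the power from n_eff = episodes/(1 + (m − 1) × ICC) using the evaluable episodes, and treat patient as the cluster in the group comparison.

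In either case, replace the claim of certainty at the start of the sample-size sentence with the alpha and power actually used. The inputs fit about 80% power at two-sided 5%, which the sponsor should confirm.

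**Cost.** If one episode per patient was always meant, the change is a sentence or two. If repeats count, the stated power becomes less favourable, and the sponsor must defend an assumed ICC. If repeats were meant to count and the sponsor now chooses one per patient, 55 evaluable patients per group are needed. Had the plan been about two episodes each, 55/2 gives roughly 28 patients, and their first episodes alone would give only about 51% power.
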